7.10.4 CCI

CCI

CCI

7.10.5 Characterization of Humoral Immune Response

Data on characterization of the humoral immune response will be summarized descriptively by vaccine received based on the PPS.

7.10.6 Cell-Mediated Immunity Response

Subjects in the CMI subset of the PPS will have their CMI response summarized descriptively by vaccine received.

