6.1 Trial Design

This is a descriptive, Phase II, double-blind, randomized, and controlled trial in 400 subjects aged 21 to 45 years living in Singapore. Subjects will be randomized (1:1) into two treatment arms:

- Arm 1 will receive one subcutaneous (SC) dose of HD-TDV;
- Arm 2 will receive one SC dose of TDV.

Randomization will be stratified based on the dengue IgG status (positive / negative) at screening, resulting in four investigational groups ([Figure 6.a](#)).

[figure not shown]
Figure 6.a Den-205 schematic showing the stratified randomization process

^aApproximately 40 subjects in each of the IgG positive and negative groups will form the CMI subset.

Subjects will be followed for one year, with 13 scheduled visits, for the assessment of reactogenicity, safety and/or immunogenicity ([Figure 6.b](#)). Cell-mediated immunity will be assessed in a subset of approximately 80 subjects (approximately 40 subjects in each of the IgG positive and negative groups). This CMI subset will consist of volunteers identified at the time of randomization.

Figure 6.b DEN-205 schematic showing subject flow through the trial

Immunogenicity evaluation:

- Neutralizing antibodies (MNT) will be measured on blood samples collected pre-vaccination on Day 1 (Month 0) and post-vaccination on Days 15, 30 (Month 1), 90 (Month 3), 180 (Month 6) and 365 (Month 12).

Assessment of viral replication:

- Vaccine viremia will be assessed on blood samples collected pre-vaccination on Day 1 (Month 0) and post-vaccination on Days 5, 7, 9, 11, 15, 17, 21 and 30 (Month 1).

Safety evaluation:

- Subjects will be provided with a diary card for the recording of:
 - Solicited local AEs for 7 days following vaccination (day of vaccination + 6 days). These will include: injection site pain, injection site erythema, and injection site swelling.
 - Solicited systemic AEs for 14 days following vaccination (day of vaccination + 13 days). These will include: fever, headache, asthenia, malaise, and myalgia.

CONFIDENTIAL

- Unsolicited AEs for 28 days following vaccination (day of vaccination + 27 subsequent days).
- Serious adverse events throughout the trial.

Exploratory assessments:

• CCI

- Neutralizing and non-neutralizing antibodies will be characterized on blood samples collected pre-vaccination on Day 1 (Month 0), and post-vaccination on Days 30 (Month 1), 60 (Month 2), 90 (Month 3), 180 (Month 6) and 365 (Month 12) by different exploratory assays.

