6.2 Justification for Trial Design, Dose, and Endpoints

The trial design and the collection of solicited and unsolicited AEs following vaccination are consistent with vaccine evaluation studies.

Data generated to date show substantial increases in GMTs of dengue neutralizing antibodies to all four serotypes after a single dose of HD-TDV, with the highest titers being to DEN 2. There was a limited increase in titer following a second dose given at 3 months after the first. Therefore, a single dose regimen is being evaluated in trial DEN 204 and used in the present trial.

The rationale for a reduced dosage of TDV-2 is based on data from previous Phase I trials with HD-TDV (DEN-101, -102 and -104) which showed a consistently greater immune response and frequency of vaccine viremia for TDV-2 than for the three other dengue vaccine strains, suggesting a greater potential for TDV-2 to replicate. This TDV-2 replication may theoretically inhibit replication of the other serotypes, interfering with the immune response.

Prior dengue infection may influence immune responses elicited by TDV as well as may have an impact on vaccine viremia due to the four dengue vaccine strains. Therefore, the trial will be conducted in a dengue semi-endemic country allowing characterization of humoral immune responses following vaccination with a prophylactic dengue vaccine when given to both dengue

CONFIDENTIAL

naïve and dengue pre-exposed subjects. In addition, CMI will be characterized in a subset of subjects (approximately 80 subjects), referred to as the CMI subset.

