8.3 Randomization Code Creation and Storage

Randomization personnel of the Sponsor or designee will generate the randomization schedule. Randomization information will be stored in a secured area, accessible only by authorized personnel.

Randomization will be stratified by baseline dengue IgG status (positive / negative) measured by dengue IgG indirect ELISA performed on blood sample collected at screening. Inclusion in the CMI subset (approximately 80 subjects) will be on a voluntary basis.

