13.1.3 Immunogenicity Analysis

For primary and secondary immunogenicity endpoints (i.e., GMTs of neutralizing antibodies and seropositivity rates [%] for each of the four dengue serotypes, descriptive statistics and 95% confidence intervals (CIs) will be provided by treatment arm (overall), and by treatment arm and baseline dengue seropositivity (MNT) for each applicable visit. Seropositivity is defined as a reciprocal neutralizing titer ≥ 10 .

CMI data will be summarized descriptively.

CONFIDENTIAL

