7.2 Analysis Sets

Randomized Set: The Randomized Set will consist of all randomized subjects. Subjects will be summarized according to vaccine received.

Safety Set: The Safety Set will consist of all randomized subjects who received the study vaccine (TDV or HD-TDV). Subjects will be summarized according to vaccine received.

Full Analysis Set (FAS): The FAS will consist of all randomized subjects who received the study vaccine (TDV or HD-TDV) and for whom a valid pre-dose and at least one valid post-dose blood sample are taken. Subjects will be summarized according to vaccine received.

Per-Protocol Set (PPS): The PPS will consist of subjects in the FAS who have no major protocol violations as presented in [Table 7.a](#). The major protocol violation criteria will be defined as part of the blinded data review prior to the unblinding of subject's vaccine assignment. The categories of major protocol violations include: (1) not meeting selected entry criteria, (2) receiving wrong study vaccine except for the packaging issue noted below, (3) receiving prohibited therapies, and (4) other major protocol violations that may be identified during blinded data reviews. Any changes to these criteria after approval of the SAP will be documented and approved in a separate document (blinded data review meeting minutes) prior to database lock and unblinding. Subjects will be summarized according to vaccine received.

Cell-Mediated Immunity Subset (CMI): Cell-mediated immunity will be assessed in a subset of approximately 80 subjects (approximately 40 subjects in each of the IgG positive and negative groups). The CMI subset is a subset of the PPS and will consist of subjects identified at the time of randomization. Subjects will be summarized according to vaccine received.

Background for summarizing data based on the vaccine received instead of randomized vaccine:

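### SAP 7.10.5 and 7.10.6 specify no split by baseline serostatus for the humoral-characterization and CMI summaries, although the design was built around naive and pre-exposed subjects

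*SAP*

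**What the plan says.** **The two sections at issue.** SAP 7.10.6 states: "Subjects in the CMI subset of the PPS will have their CMI response summarized descriptively by vaccine received". SAP 7.10.5 states: "Data on characterization of the humoral immune response will be summarized descriptively by vaccine received based on the PPS". Neither mentions baseline serostatus or the screening IgG stratum. The general rules in SAP 7.1 and 7.1.1 do not add a split. Protocol 13.1.3 says only that "CMI data will be summarized descriptively".

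**Where the SAP does split.** The PPS analyses of MNT antibody are repeated by baseline serostatus (7.10.2, and the plots in 7.10.1). Viremia is shown overall and by serostatus (7.10.3). So are disposition (7.3), demographics (7.4) and the main adverse-event summaries (7.11.1).

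**What the design says.** Protocol 6.1 stratifies randomization by screening IgG and composes the CMI subset of "approximately 40 subjects in each of the IgG positive and negative groups". Protocol 4.2 says the trial will compare the two formulations in naive and previously exposed subjects. Protocol 6.2 gives the reason: "Prior dengue infection may influence immune responses elicited by TDV as well as may have an impact on vaccine viremia". It goes on to say that a semi-endemic country was therefore chosen so that humoral responses can be characterized in both kinds of subject.

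**The concern.** A naive subject and a previously infected subject may respond differently to the vaccine, and the protocol says so. If CMI and exploratory antibody results are tabulated by vaccine only, each mean is a weighted average of two populations. For CMI the weights come from how the subset was filled, not from any population of interest. Such a mean describes neither group, and a difference between formulations that exists in only one group is diluted. Protocol 13.1 leaves it to the SAP to set out the methods for all trial objectives, and these two are among them. If the SAP does not name the split, any serostatus table added later is post hoc.

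**Working it through.** **Inputs**
- CMI subset: about 80 subjects, about 40 per IgG group (Protocol 6.1, SAP 7.2). Check: 40 + 40 = 80, which reproduces the stated size.
- Allocation: 1:1 within IgG stratum (Protocol 6.1, 8.3).
- Entry: "Inclusion in the CMI subset (approximately 80 subjects) will be on a voluntary basis" (Protocol 8.3).
- Gap d between stratum means, in within-stratum SDs: not in the documents. Assumed d = 1 to 2.
- Assumed for the main figures: an even vaccine split within each IgG group, equal within-stratum SDs, and IgG status agreeing with MNT serostatus.

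**Cell sizes.** 80 / 2 vaccines = 40 per CMI summary; 40 / 2 = 20 IgG-positive and 20 IgG-negative within each.

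**Position of the pooled mean.** With weights of 1/2 it lies d/2 from each stratum mean: 0.5 SD at d = 1 and 1.0 SD at d = 2.

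**Dilution of a vaccine difference.** If the difference is D in one stratum and 0 in the other, the pooled difference is 0.5 × D + 0.5 × 0 = D/2.

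**Precision, pooled against split.** These sections plan no confidence intervals; half-widths are used only as a yardstick.
- Pooled SD for a 20/20 mix = sqrt(38/39 + (d²/4)(40/39)).
- Pooled 95% half-width = t(0.975, 39) × pooled SD / sqrt(40).
- Single-cell half-width = t(0.975, n − 1) / sqrt(n).

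| Summary | SD (within-stratum units) | 95% half-width |
|---|---|---|
| Pooled n = 40, d = 1 | 1.109 | 0.355 |
| Pooled n = 40, d = 2 | 1.414 | 0.452 |
| Single cell n = 20 | 1 | 0.468 |
| Single cell n = 15 | 1 | 0.554 |
| Single cell n = 10 | 1 | 0.715 |

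Splitting does not narrow the interval: it is slightly wider at d = 2 and clearly wider at d = 1.

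**Chance imbalance.** If the vaccine split among 40 volunteers in a stratum behaves as Binomial(40, 0.5), the 95% range for one arm is 14 to 26. With 14/26 in one stratum and 20/20 in the other, the second stratum's share of each arm is 20/34 and 20/46. The pooled arm difference then shifts by 20/34 − 20/46 = 0.153 SD per 1 SD of gap. A split summary does not have this shift.

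**Humoral summary.** Let p be the seropositive share of the PPS. The pooled mean lies (1 − p)d from the seropositive mean and p × d from the seronegative mean. No readable passage fixes p, so no number is given.

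**The case against.** The strongest case against acting has four parts.

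**No commitment is breached.** The secondary objectives name baseline serostatus; the exploratory humoral and CMI objectives do not. Protocol 13.1.3 asks only for a descriptive CMI summary. A reader might infer from Protocol 4.2, which speaks of analyzing trial endpoints by baseline seropositivity, that every endpoint must be split. That sentence's job is to say which assay classifies subjects (MNT rather than IgG), so it does not carry that reading. This objection stands.

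**The split is not unique in being absent.** It is tempting to say that every other immune analysis is split. That cannot be shown: SAP 7.10.4 is redacted, and the supportive analysis on the full analysis set (7.10.1) is not repeated by serostatus. It is also fair to say that the humoral aim in Protocol 6.2 is partly met by the MNT results, which are split.

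**The purpose of the 40/40 composition is not stated.** Separating naive from exposed subjects is a natural inference alongside Protocol 4.2 and 6.2, but no passage says so. The reason given in Protocol 4.2 for studying CMI in these adults is blood volume and sample handling. Nor does the 40/40 figure extend to the humoral data, which use the whole PPS.

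**The harm can be overstated.** A reader might infer that pooling widens confidence intervals. None are planned in these sections, and the table above shows that splitting would not narrow them. No formal arm contrast is planned either. Serostatus is measured in everyone and all data are listed (SAP 7.1.1), so the split could still be produced later.

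What remains is that the tables specified for these two endpoints mix two populations that the protocol itself expects may differ. Later production is possible, but it would not be prespecified.

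**Conclusion.** The point holds as an omission: SAP 7.10.5 and 7.10.6 specify grouping by vaccine received only. The SAP does not forbid a serostatus split; it does not provide one.

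For CMI, under an assumed stratum gap of 1 to 2 within-stratum SDs and an even vaccine split, the pooled mean sits 0.5 to 1 SD from either stratum's mean. A vaccine difference confined to one stratum shows at half its size. If the true gap is small, the loss is small. For the humoral characterization the same reasoning applies, but at the unknown serostatus mix of the PPS.

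Severity is low. Both endpoints are exploratory, the trial is descriptive throughout, and the primary analysis is not touched.

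**What to change.** In SAP 7.10.5 and 7.10.6, adopt the grouping already used in 7.10.3: vaccine received, shown overall and by baseline seropositivity status on MNT, with n in each cell. For the CMI subset, a further split by screening IgG stratum is optional, since its composition was set on IgG.

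The cost is a wording change and by-group runs of tables already planned, with no new data. The downside is small CMI cells. They should be about 20, but may be fewer: entry is voluntary, the subset is restricted to the PPS, and recruitment was by IgG while the subgroup is by MNT. Showing n lets the reader judge this.

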7.11 Safety Analysis

All summaries of safety data will be performed using the Safety Set. The safety data will be summarized by vaccine received.

7.11.1 Adverse Events

Reactogenicity (Solicited adverse events [AEs])

Subjects are provided with a diary card for the recording of solicited local AEs, including injection site pain, injection site erythema, and injection site swelling, for 7 days following vaccination (day of vaccination + 6 days). Subjects are also provided with a diary card for the recording of solicited systemic AEs (fever, headache, asthenia, malaise, and myalgia) for 14 days following vaccination (day of vaccination + 13 days). Any solicited local or systemic AE observed as continuing on study Day 7 (local reactions) or Day 14 (systemic reactions) will be recorded as an unsolicited AE on the AE eCRF. Any solicited local or systemic AE that resolved before that time but which recurs at a later time will be recorded as an unsolicited AE on the AE eCRF. The details of solicited local and systemic AEs, severity of solicited safety parameters are given in [Appendix B](#).

For each solicited AE, the number of subjects and the percentage of subjects will be summarized by event severity:

- 30 minutes after study vaccination
- for each day (Days 1 to 7 after vaccination for local AEs, and Days 1 to 14 after vaccination for systemic AEs) and overall (within 7 days after vaccination for local AEs, within 14 days after vaccination for systemic AEs)
- for Day 1 to Day 3 and Day 4 to Day 7 for local AEs, Day 1 to Day 7 and Day 8 to Day 14 for systemic AEs

For subjects with more than 1 episode of the same event, the maximum severity will be used for tabulations.

For solicited systemic AEs, the number and percentage of subjects will also be summarized by relationship:

- 30 minutes after study vaccination
- Within 14 days after vaccination

Subjects will only be counted once if the subject has more than 1 episode of the same event. In the case where the subject has both related and unrelated AEs, the subject will be counted under the related category.

The number of subjects who had their first onset of each event will be provided for each day. The total number of days for each AE term will also be summarized.

Additional subgroup analyses of AE severity will be performed by baseline seropositivity status (seropositive for at least 1 dengue serotype/seronegative for all dengue serotypes) for summaries of solicited local AEs 30 minutes after study vaccination, solicited systemic AEs 30 minutes after study vaccination, solicited local AEs within 7 days after study vaccination, and solicited systemic AEs within 14 days after study vaccination. Solicited local AEs within 7 days after study vaccination and solicited systemic AEs within 14 days after study vaccination will also be repeated by occurrence of viremia (subjects with viremia /subjects without viremia).

Additional subgroup analyses of AE relationship to study vaccine will be performed by baseline seropositivity status for summaries of solicited systemic AEs 30 minutes after study vaccination and solicited systemic AEs within 14 days after study vaccination. A summary of solicited systemic AEs within 14 days after study vaccination by relationship will also be performed by subgroup of occurrence of viremia.

For solicited AEs, missing data will be handled as follows. For each vaccine group and solicited AE, the denominator for the percentage will exclude subjects with completely missing data (i.e. subject does not have at least one recorded result of none, mild, moderate, or severe) for the solicited AE in the period being summarized.

Prolonged solicited AEs that continue beyond Day 7 (for local AEs) or Day 14 (for systemic AEs) will be identified during the blinded data review based on the question “Did the symptom continue beyond Day 7/14?” and start/end dates of the corresponding unsolicited AEs. These prolonged solicited AEs will be presented in a separate listing.

Unsolicited AEs and Serious Adverse Events (SAEs)

Any AE identified as a prolonged solicited AE will not be included in any unsolicited AE summary or listing.

Unsolicited AEs will be assessed for 28 days following vaccination (day of vaccination + 27 subsequent days). Collection of SAEs will commence from the time that the subject is vaccinated (Day 1 [Month 0]). Routine collection of SAEs and AEs leading to discontinuation from study will continue until the end of the study (Day 365 [Month 12]). Unsolicited AEs and SAEs will be coded according to MedDRA and summarized by SOC and PT.

In general, the number of events, number of subjects, and the percentage of subjects will be tabulated at each of the following levels: overall summary (any adverse events/ subjects with any adverse events) and by SOC and PT. Subjects reporting more than 1 occurrence for the term

(level) being summarized will be counted only once in the number/percentage of subjects. Unsolicited AEs will be summarized as follows: by SOC; by SOC and PT; by PT; including only non-serious events with frequency greater than 2% ($>2\%$ of subjects in any vaccine group in order to provide this information for Clinicaltrials.gov); by SOC, PT, and relationship to the study vaccine; by SOC, PT, and severity; and by SOC, PT, and outcome. Study vaccine-related AEs will be summarized by SOC, PT; by SOC, PT, and severity; and by SOC, PT, and outcome.

Unless otherwise specified, unsolicited AEs will be summarized for the following 3 time periods:

1. Overall up to 28 days post-vaccination (onset between 1 and 28 days post-vaccination)
2. With onset between 1 and 14 days post-vaccination
3. With onset between 15 and 28 days post-vaccination

SAEs will be summarized as follows: by SOC and PT; by SOC, PT, and relationship to the study vaccine; and by SOC, PT, and outcome.

AEs leading to study discontinuation will be summarized by SOC, PT.

Additional subgroup analyses will be performed by baseline seropositivity status (seropositive for at least 1 dengue serotype/seronegative for all dengue serotypes) as well as for occurrence of viremia for overviews and summaries of unsolicited AEs, serious AEs, and AEs leading to study discontinuation; summaries of study vaccine-related AEs; relationship to the study vaccine of serious AEs.

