7.10.3 Vaccine Viremia Analysis

Vaccine Viremia is defined as a positive result from the Dengue Vaccine Screening Reverse Transcription-Polymerase Chain Reaction (RT-PCR).

The vaccine viremia endpoints of the study are the vaccine RNA level, incidence, and duration, of vaccine viremia for each of the four TDV strains (TDV-1, TDV-2, TDV-3, TDV-4) post-vaccination.

Vaccine viremia will be assessed on blood samples collected pre-vaccination on Day 1 (Month 0) and post-vaccination on Days 5, 7, 9, 11, 15, 17, 21 and 30 (Month 1).

Vaccine viremia summaries will be presented by vaccine received and visit, overall and by baseline seropositivity status (seropositive for at least 1 dengue serotype/seronegative for all dengue serotypes) based on the Safety Set.

The number of subjects with non-missing assessment, mean, associated 2-sided 95% confidence interval (CI) and associated SD, median, minimum, and maximum will be presented for vaccine RNA (vRNA) levels (expressed as \log_{10} [genome equivalents per mL]) measured by RT-PCR for each TDV strain.

Incidence rates of vaccine viremia along with exact 2-sided 95% CI, will be presented for each TDV strain. The exact 2-sided 95% CI of incidence rate will be calculated based on the Clopper-Pearson method.

The duration of vaccine viremia for each serotype = visit date when vaccine viremia is last detected (positive result) – visit date when vaccine viremia is first detected (positive result) + 1 day. For the number of subjects with non-missing assessment, mean, associated 2-sided 95% confidence interval (CI) (based on student's t-distribution) and associated SD, median, minimum, and maximum will be presented. The number and percentage of subjects with different categories of vaccine viremia duration will also be presented. In addition, the number of days to onset of viremia will be summarized descriptively and categorized for TDV strain.

Samples that are positive in the Dengue Vaccine Screening RT-PCR will undergo the Vaccine Confirmation Sequencing assay to determine the nucleotide at three attenuation loci sites.

Summaries for each TDV strain will include the following categories: No loci with possible reversion, 1 locus with possible reversion, 2 loci with possible reversion, and all loci with possible reversion.

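### The SAP's adverse-event-by-viremia tables are not split by baseline serostatus, so a serostatus difference can appear as a viremia association of either sign; the viremia flag also lacks a period and a sampling rule

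*SAP*

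**What the plan says.** SAP 7.11.1 takes the solicited AE summaries by severity (local within 7 days, systemic within 14 days) and states that they "will also be repeated by occurrence of viremia (subjects with viremia /subjects without viremia". For solicited systemic AEs, a summary "by relationship will also be performed by subgroup of occurrence of viremia". For the remaining AE summaries, baseline seropositivity is named as a subgroup factor, "as well as for occurrence of viremia for overviews and summaries of unsolicited AEs, serious AEs, and AEs leading to study discontinuation"; vaccine-related AEs are included too. Serostatus and viremia stand side by side as two factors, and no table crosses them. Under SAP 7.11 all safety data are summarized by vaccine received, so the vaccine groups stay separate.

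SAP 7.10.3 gives the only definition: "Vaccine Viremia is defined as a positive result from the Dengue Vaccine Screening Reverse Transcription-Polymerase Chain Reaction (RT-PCR". Samples are taken before vaccination and "post-vaccination on Days 5, 7, 9, 11, 15, 17, 21 and 30 (Month 1". Local AEs are solicited "for 7 days following vaccination (day of vaccination + 6 days" and systemic AEs "for 14 days following vaccination (day of vaccination + 13 days". Nothing says over which period a positive result counts, whether one positive strain is enough, or how a subject with missed samples is classed.

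Protocol 6.2 states: "Prior dengue infection may influence immune responses elicited by TDV as well as may have an impact on vaccine viremia". The trial recruits both naive and pre-exposed adults and stratifies randomization by screening IgG. Protocol 13.1.5 plans safety by arm and, for key tables, by arm and serostatus. The viremia split is an addition in the SAP.

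**The concern.** A variable linked to both viremia and AEs, and left out of the table, produces an association between them. The protocol expects serostatus to matter for viremia, and the SAP reports AEs by serostatus as well, so it treats serostatus as potentially relevant to both. Splitting by vaccine received does not help, because naive and pre-exposed subjects are mixed within each vaccine group.

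These are the only planned tables shown in the documents that relate vaccine viremia to AEs. A reader who sees more reactions in viremic subjects will tend to credit viremia, and a reader who sees no difference will tend to dismiss it. Either conclusion could be wrong. The undefined flag adds a second difficulty: nothing ties a subject's viremia result in time to the AE being counted.

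**Working it through.** The plan gives no figure on this point and rests on no power calculation, so there is nothing to reproduce. Three checks follow.

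**1. Serostatus.** Consider one vaccine group. Let p be a serostatus share, v the viremia rate and a the AE rate in that serostatus, with no viremia effect within either serostatus. Then:

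- AE rate in viremic subjects = Σ p·v·a / Σ p·v
- AE rate in non-viremic subjects = Σ p·(1−v)·a / Σ p·(1−v)

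All rates are assumptions. Worked case: half seropositive, viremia 60% in seronegative and 10% in seropositive subjects, AE 60% and 30%.

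- Viremic: (0.5×0.6×0.6 + 0.5×0.1×0.3) / 0.35 = 0.195 / 0.35 = 55.7%
- Non-viremic: (0.5×0.4×0.6 + 0.5×0.9×0.3) / 0.65 = 0.255 / 0.65 = 39.2%
- False difference: +16.5 points

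Other inputs (differences taken before rounding):

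| Seropositive share | Viremia, seroneg./seropos. | AE, seroneg./seropos. | AE, viremic | AE, non-viremic | False difference |
|---|---|---|---|---|---|
| 50% | 60/10% | 50/30% | 47.1% | 36.2% | +11.0 |
| 50% | 60/10% | 50/40% | 48.6% | 43.1% | +5.5 |
| 50% | 60/10% | 30/60% | 34.3% | 50.8% | −16.5 |
| 30% | 40/20% | 50/40% | 48.2% | 46.4% | +1.9 |
| 70% | 80/5% | 60/30% | 56.2% | 32.5% | +23.7 |
| 50% | 30/30% | 60/30% | 45.0% | 45.0% | 0 |
| 50% | 60/10% | 40/40% | 40.0% | 40.0% | 0 |

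The grid covered seropositive shares of 30 to 70% and viremia contrasts from 40/20% to 80/5%. Where both rates differ by serostatus, the absolute false difference ran from about 2 to 24 points. Within a serostatus stratum it is zero by construction.

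**2. Timing, on nominal visit days.** The first post-dose sample is on Day 5, so Days 1 to 4 have none:

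- Local AEs: 4 of 7 days (57%); 6 of the 8 post-dose samples fall after the window.
- Systemic AEs: 4 of 14 days (29%); 4 of 8 samples fall after the window.
- Unsolicited AEs: 4 of 28 days (14%); 1 of 8 samples falls after the window.

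Let e be the rate of early AEs, unrelated to viremia, and l the rate of later AEs. Then P(any AE) = 1 − (1−e)(1−l).

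- No viremia effect, e = 0.3, l = 0.2 in both groups: 44% against 44%. No false difference arises.
- Real later effect, l = 0.4 against 0.2, e = 0.3: 1 − 0.7×0.6 = 58% against 1 − 0.7×0.8 = 44%. A 20-point difference (ratio 2.0) shrinks to 14 points (ratio 1.32).
- Same effect, e = 0.5: 70% against 60%, ratio 1.17.

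Counting only later AEs in both groups returns 40% against 20%.

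**3. Precision cost of stratifying.** Take 200 subjects per vaccine group (Protocol 2.0), an assumed 40% AE rate and 70 viremic against 130 non-viremic subjects. The 95% half-width for the difference is 1.96 × √(0.24/70 + 0.24/130) = 14 points. If each stratum holds half of both groups, it is 1.96 × √(0.24/35 + 0.24/65) = 20 points. With viremia at 60% and 10% in strata of 100, the seronegative stratum has 60 against 40 subjects, giving 1.96 × √(0.24/60 + 0.24/40) = 20 points. The seropositive stratum has 10 against 90, giving 1.96 × √(0.24/10 + 0.24/90) = 32 points.

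**The case against.** The best case against the point is that little depends on these tables. SAP 7.1 calls all analyses exploratory, no test or confidence interval is planned for the AE tables, and no objective concerns a relation between AEs and viremia. AEs by serostatus and viremia by serostatus are both reported, so a reader can see whether the two conditions for confounding are met. Unless otherwise specified, unsolicited AEs are also split by onset on Days 1–14 and 15–28, and all data are listed. This lowers the priority. It does not remove the point, because two separate tables by serostatus do not give the AE rates by viremia within serostatus.

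A reader might also infer stronger things that the documents do not support:

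- **AEs that precede viremia create a false viremia effect.** Check 2 shows that they dilute a real one unless something shared, such as serostatus, links early AEs to later viremia.
- **The SAP counts a positive result at any time to Day 30.** That is the natural reading, but no period is stated.
- **Subjects who leave early are classed as without viremia.** No such rule exists; their handling is simply not specified. AEs leading to discontinuation are collected to Day 365, so many who leave could have a full sampling series.
- **The tables bear on why serotype 2 potency was lowered.** Protocol 4.2 and 6.2 give possible interference with the immune response to the other serotypes as the reason. Reactogenicity is not mentioned in that reason.

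**Conclusion.** The point holds in a limited form. The AE-by-viremia tables leave out a variable that the protocol itself expects to influence viremia. They can therefore show an association that is only serostatus, about 2 to 24 points in absolute value over the assumed rates. Its size and sign cannot be known from the documents: Protocol 6.2 says only that prior infection may affect viremia, and nothing says that AE rates differ by serostatus. If either rate does not differ, the false association is zero.

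The undefined flag and the unsampled first four days are a secondary weakness. They blur a real contrast and prevent any reading of viremia followed by AE, but they do not by themselves produce a false signal. The tables are descriptive and were not called for by the protocol, so the priority is low to moderate.

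**What to change.** In SAP 7.11.1, present the main AE-by-viremia tables (solicited local, solicited systemic, any unsolicited AE) by vaccine received within baseline seropositivity status, or at least in baseline-seronegative subjects.

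Secondarily:

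- Define occurrence of viremia: the period, that a positive result for any strain counts, and the minimum samples needed to be classed as without viremia. Show the rest as not evaluable.
- Add a comparison restricted to AEs with onset from Day 5 in both viremia groups, so that the periods match. Splitting AEs before and after the first positive sample in viremic subjects alone would leave no comparison period in the others. Ending the flag at the Day 15 visit would still count a positive sample scheduled after the Day 1–14 window.
- Label the tables as association only. Even with onset from Day 5, an AE can come before the first positive sample.

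The cost is SAP text and table shells, since all the data are already collected. Cells will be small, especially for viremic seropositive subjects, and half-widths grow from about 14 points to about 20, or more in the smaller stratum. The Day 5 restriction leaves 3 of the 7 local AE days.
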